A total of one hundred participants will be recruited from the University of North Carolina (UNC) School of Dentistry (SOD) Graduate Prosthodontics clinic, Graduate Operative clinic, and the Dental Faculty Practice. A stratified block randomization will be used to randomize patient to impression technique: Aquasil Ultra Cordless, Dentsply International using Aquasil Ultra Polyvinyl siloxane (PVS) impression material versus Dentsply International, gingival displacement cord (Ultrapak, Ultradent Products International) hydrated with aluminum chloride hexahydrate (Hemodent, Premier Dental Products Company). Stratification will be based on the clinic where treatment is provided (Dental Faculty Practice, Graduate Operative Dentistry, Graduate Prosthodontic Clinic). A block size of 4 within each stratum will be used to maintain a balanced allocation to impression group. The randomization schedule will be prepared by [name]. Randomization allocations will be placed in sequentially numbered envelopes for ease of use by clinicians within the three clinics.

The treating clinician will open the allocation envelope after the tooth preparation is completed. This is to limit the potential bias of the clinician altering the tooth preparation design in anticipation of a known gingival displacement technique. Although the patient may require restorations on multiple teeth, only one tooth, the most posterior, will be included in the evaluation. The clinician will be instructed to

complete the impression for that tooth before proceeding to other teeth. The patient will be informed that participation, if multiple teeth are treatment planned, may increase the appointment time.

The gingival displacement procedures and impression procedures are described here:

Traditional Corded Impression Procedure:

- 1) The prepared tooth is washed and dried, and assure hemostasis.

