- 2) Small diameter retraction cord, after it has been hydrated with Hemodent for 10 minutes, is tucked around the tooth in the space between it and its surrounding gum tissue. A second larger diameter retraction cord, also hydrated with Hemodent, will be placed over the first cord and tucked around the tooth. These cords will be left in place for a minimum of 8 minutes. These cords temporarily push the gum tissue back away from the tooth. (Before making the impression, the 2nd larger cord is removed, and the gums will stay back long enough for the impression material to seep around the tooth, thus allowing it to capture a copy of the entire tooth preparation.)
- 3) After a minimum of 8 minutes, the larger 2nd cord will be removed, and the tooth dried. Quickly, after confirmation of a dry field, the light body consistence impression material is syringed around the prepared tooth and across the occlusal surfaces of adjacent teeth.
- 4) An impression tray that has been filled with the heavy body consistency impression material is then placed over the arch of teeth, and gently pressed into place to ensure the teeth are completely covered with a uniform thickness of impression material. As the different impression material consistencies set, they fuse together into a single unit.
- 5) When removed from the mouth, the impression should contain a negative copy of both the prepared tooth and the teeth of that jaw.

Cordless Impression Procedure:

- 1) The prepared tooth is washed and dried, and assure hemostasis.
- 2) Apply B4 + surface optimizer.
- 3a) If 1 prepared tooth requiring an indirect restoration is being impressed, a single size (0.7mL) unit dose cartridge will be inserted into the digit power dispenser. If more than 1 prepared tooth requiring an indirect restoration is being impressed, a multi size (1.6mL) unit dose cartridge will be inserted into the digit power dispenser.
- 3b) Using the digit power dispenser, unit dose cartridge, and intrasulcular mixing tip, depress foot pedal and gently insert tip into the gingival sulcus of the prepared tooth, slightly apical to the preparation finish line. Material should flood the sulcus. Make sure to dispense material ahead of the intrasulcular tip, and completely around the prepared finish line, and then the tooth.

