- 4) An impression tray that has been filled with the heavy body consistency impression material is then placed over the arch of teeth, and gently pressed into place to ensure the teeth are completely covered with a uniform thickness of impression material. As the different impression material consistencies set, they fuse together into a single unit.
- 5) When removed from the mouth, the impression should contain a negative copy of both the prepared tooth and the teeth of that jaw.

The clinician will record the impression technique, type of impression material used; whether tray adhesive was used; the tray material; the type of tray used; the number of units requested; the time required to obtain the first impression (start and end of impression taking is defined above for each procedure), and the total number of impressions produced until an adequate impression was made. Also recorded will be the clinic and resident year if placed in a graduate clinic and the subject's age and sex. Unique id numbers not related to clinical record will be used.

The impressions will be photographed, digitally scanned, saved in black and white, and then collectively evaluated at a later time based on a criteria evaluation form by two calibrated evaluators. The evaluators (also referred to as expert examiner) will assess each impression for errors in the finish line; in the tray/material; and errors with gingival displacement/hemostasis as primary outcomes. The number of errors can range from 0 to 13.

Patient discomfort will be assessed using the FACES visual picture pain scale rated from 1-10 based on the following question posed at 4 points during treatment; "How much discomfort are you experiencing at this point in treatment?" This question will be asked at the beginning of the treatment appointment, immediately before the impression procedure is initiated, immediately after the impression procedure is completed, and again at the completion of the treatment appointment. Each question will be rated on a scale of 1 to 10. The total score indicated by the sum of the 4 questions will be analyzed.

Patient consent will be obtained prior to treatment and the impression. This may occur at a prior treatment planning visit or at the treatment visit.

Inclusion Criteria:

- Patients must be adult males or females 18 years of age or older.
- Patients must be able and willing to follow study procedures and instructions.

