GingiBraid retraction cord	12 containers- sizes: 00,0,1,2; (3) of each.	Included in normal clinic treatment
Hemodent	3 bottles + 1 for practice calibration	Included in normal clinic treatment
Viscostat	60 disposable vial/syringe	Included in normal clinic treatment
Impression trays	60 trays + 20 for practice calibration	Included in normal clinic treatment
Impression tray adhesive	3 bottles + 1 for practice calibration	Included in normal clinic treatment
Estimate Total:		

Timeline

The study is planned to last approximately 1.5 years to allow for recruitment and data collection and analysis. The study would ask the participants to come to 2 appointments; it might be possible to consent the patient and perform treatment on the same day, if the patient was scheduled for treatment that day already.

TO BE COMPLETED BY TREATING CLINICIAN:

Patient did not meet inclusion/exclusion criteria and is dropped from the study

Medical/smoking

Probing pocket depths around treatment tooth/teeth of greater than 4mm.

Bleeding on probing around treatment tooth/teeth.

The prepared finish line is greater than 1mm sub-gingival

Patient meets inclusion/exclusion criteria

Patient ID: _____

Impression Group: _____ *Corded* _____ *Cordless*

Clinic: _____ *Dental Faculty Practice*

_____ *Graduate Operative Clinic* _____ *1st* _____ *2nd* _____ *3rd*

_____ *Graduate Prosthodontic Clinic* _____ *1st* _____ *2nd* _____ *3rd*

Patient Age: _____

Gender: _____ *Male* _____ *Female*

Type of impression material used:

Tray adhesive used:

Aquasil Ultra Cordless

Aquasil Ultra

Yes *No*

Tray material:

Metal stock *Plastic stock* *Custom* *Plastic dual arch* *Metal dual arch*

Type of tray used:

Ant quad *Post quad* *Full arch*

Number of units requested:

2-3 FDP *Onlay* *Single crown x _____*

Anterior *Canine* *Premolar* *Molar*

Jaw: *Maxillary* *Mandibular*

Time Required for 1st Impression: _____ minutes and seconds

Number of Impressions Required to Obtain Adequate Impression: _____

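### With several prepared teeth, the plan leaves open what the timed impression contains, and one of the four summed discomfort ratings follows work outside the study impression

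*Combined protocol and SAP*

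**What the plan says.** - **Index tooth (Methods).** When a patient needs several restorations, "only one tooth, the most posterior, will be included in the evaluation", and the clinician is to "complete the impression for that tooth before proceeding to other teeth". Patients are told that "participation, if multiple teeth are treatment planned, may increase the appointment time", so other teeth may be treated at the same visit.
- **Cordless Impression Procedure, step 3a.** "If more than 1 prepared tooth requiring an indirect restoration is being impressed, a multi size (1.6mL) unit dose cartridge will be inserted". The corded steps deal with one prepared tooth; in step 3 "the light body consistence impression material is syringed around the prepared tooth and across the occlusal surfaces of adjacent teeth".
- **Treating clinician's form.** It has one time field, for the first impression, and a field "Number of units requested" that allows a two- or three-unit prosthesis or several single crowns.
- **Time (Methods).** The time outcome is for the first impression. Its start and end are said to be given in the procedure descriptions, but no step is marked as either.
- **Additional impressions (Methods).** Only the first impression is evaluated. The number of impressions is recorded, but not the technique used for later ones.
- **Discomfort (Methods).** The question is asked at the start of the visit, just before the impression procedure, just after it, and "again at the completion of the treatment appointment". The sum of the four ratings is a primary outcome.
- **Statistical Analysis.** The primary test is an unadjusted Wilcoxon rank-sum test. The adjusted Poisson models name clinic, jaw and procedural materials as covariates. The number of teeth is not among them.

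**The concern.** Primary aims 2 and 3 concern the time and discomfort of one impression procedure. If the index-tooth rule governs, no study impression needs the multi-tooth branch of step 3a, yet that step sits in the procedure written for the study. If step 3a is applied to the study impression, the recorded time covers several teeth. Only the cordless arm has this branch, so its use could differ by arm. Methods also makes adherence to the printed clinical protocol a condition for including an impression, so the ambiguity bears on which impressions count.

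The discomfort problem remains even if the index-tooth rule is followed. The last rating then comes after work on other teeth done at that visit and after any additional impression. Remakes happen after allocation and may differ in frequency between arms. Because their technique is not recorded, their contribution could not be separated afterwards.

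**Working it through.** **1. The passages side by side, for a patient with several prepared teeth**

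- *Index-tooth rule followed, step 3a used only for the remaining teeth:* the time is the index tooth's. The rating just after the impression belongs to the index tooth. The end-of-appointment rating follows the other teeth.
- *Step 3a applied to the study impression:* time, and the rating just after the impression, may reflect several teeth.
- *What would tell the two apart:* nothing collected. The units field describes the restorations requested, not the contents of the timed impression.

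**2. The plan's own figure.** Noether's formula for the rank-sum test with 1:1 allocation is N = (1.960 + 0.842)² / (3 × (0.709 − 0.5)²) = 7.849 / 0.1310 = 59.9, or 29.95 per group. The stated 30 per group reproduces (power 80.1%). It concerns total errors only, so this point does not alter it. At 50 per group (100 enrolled) the power is 95%.

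**3. Time, as an illustration.** The documents give no multi-tooth share and no SD for time. The assumptions are a normal shift of 0.78 SD (which gives P = 0.709), 10% to 50% multi-tooth patients, and other teeth adding 1 to 2 SD on average. P is the probability that a cordless time is shorter than a corded one. Each setting has at least 2,000 simulated trials.

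| Other teeth in the timed impression | P | Power, 30 per group | Power, 50 per group |
|---|---|---|---|
| None | 0.71 | 83% | 97% |
| Both arms, 10% of patients, +1 SD | 0.70 | 80% | 95% |
| Both arms, 50% of patients, +2 SD | 0.64 | 45% | 65% |
| Cordless only, 10% of patients, +1 SD | 0.68 | 70% | 91% |
| Cordless only, 50% of patients, +2 SD | 0.47 | 6.5% | 8.3% |

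The starting P is borrowed from the error outcome. If the timer covers the corded procedure's 8-minute minimum, the true time difference may be much larger and harder to mask. On a minute scale, assume 3 minutes of cord placement and 1 minute of cordless delivery per tooth. For k teeth the difference is (8 + 3k) − k = 8 + 2k, so 10 minutes for one tooth and 12 for two. With a share m of two-tooth patients in both arms it averages 10 + 2m, or 10.2 to 11.0 minutes for m = 10% to 50%, a change of 2% to 10%. If only the cordless arm takes the second tooth it averages 10 − m, or 9.9 to 9.5 minutes.

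**4. Discomfort under the index-tooth rule.** Ratings of 1 to 10 span 9 points each, so the last one supplies 9 of the sum's 36-point span, a quarter. The assumptions are four ratings of SD 1, correlation 0.3 or 0.6, a 0.78 SD effect on the rating just after the impression, none or half of it persisting to the last rating, and other teeth adding 1.5 SD to the last rating.

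- Raising the multi-tooth share from 0 to 50% moves power by at most about 6 points. The largest fall is 37% to 31% at 30 per group and 53% to 48% at 50 (correlation 0.3, half the effect persisting).
- With no multi-tooth patients, power for the sum is already only 15% to 37% at 30 per group. Summing in ratings that carry little or none of the effect costs more than the other teeth do.
- The sum has SD √(4 + 12ρ) = 2.76 or 3.35. The standardised effect is 0.28 or 0.23 with no persistence (0.78/SD), and 0.42 or 0.35 with half (1.17/SD).
- The after-minus-before difference has SD √(2(1 − ρ)) = 1.18 or 0.89. The standardised effect is 0.66 or 0.87.

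**The case against.** Step 3a is conditional. A site can take the index tooth's impression first and use the larger cartridge for the remaining teeth, so both passages can be followed. A units field that allows several restorations fits a plan that admits such patients. This stands: a reader might infer that the recorded time is not the index tooth's, but the documents support only that it cannot be confirmed.

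The envelope is opened after preparation, so the number of prepared teeth differs between arms only by chance. This also stands, and makes the effect mainly noise. It does not cover events after allocation, namely a branch present in one arm only and remakes.

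A reader might also infer that failed cordless impressions are remade with cord and that this draws the arms together. No passage says so, and a failed attempt followed by a second technique could equally raise the cordless score. Discomfort from a remake is arguably a consequence of the allocated technique, so a whole-appointment measure is a legitimate quantity. But aim 3 names the procedure, accuracy is judged on the first impression alone, and work on other teeth is not a consequence of the index-tooth impression.

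Finally, the minute-scale formula gives 14 minutes for three teeth against 10 for one, which invites talk of a 40% change. That compares a trial made up only of three-tooth patients with one made up only of one-tooth patients, on assumed times.

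**Conclusion.** The point holds in a limited form. The index-tooth rule and cordless step 3a do not fit together, and the form does not resolve it, so in multi-tooth patients the time outcome is not clearly defined. It is the index tooth's time if the Methods rule is followed. The last discomfort rating is outside the study impression in any patient whose other teeth are treated at the same visit or who has an additional impression, whichever reading applies, and it makes up a quarter of the primary score's span.

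For discomfort the added noise is small: at most about 6 points of power on the stated assumptions. For time the effect runs from nil to large, depending on an unknown multi-tooth share, on how step 3a is used and on the assumed SD. Bias between arms is possible but not shown. Patients with one prepared tooth and no remake are unaffected, as are the accuracy outcome and its stated power. In an exploratory study this justifies clarification and modest changes to the analysis; it does not show that the time or discomfort comparison is invalid.

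**What to change.** 1. Reconcile the index-tooth rule, cordless step 3a and the clinician's form on what the timed study impression contains. The investigators decide which governs.
2. Tie the existing third discomfort question to the end of the first study impression, and state that the second is asked before gingival displacement begins in both arms. Base the primary comparison on the third relative to the second: for example, the rank-sum test on the difference, and the after-rating with the before-rating as a covariate in the adjusted model, since a Poisson outcome cannot be negative.
3. Leave the fourth question where it is and report it separately as descriptive. Moving it earlier would duplicate the third.
4. Record the technique of every additional impression.
5. Add the number of teeth prepared before the envelope is opened to the adjusted models for time and discomfort. The units field nearly supplies it, but the form should say that prepared teeth are counted. Do not use the number of teeth in the study impression: it is constant under the index-tooth rule and may be decided after allocation under step 3a.
6. Repeat the time and discomfort comparisons in single-tooth patients as a sensitivity analysis, because the covariate does not enter the unadjusted primary test.

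The cost is a few form edits, one covariate and one extra analysis. The downside is that later discomfort, including that from remakes, leaves the primary score and is reported only descriptively.

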More effective and efficient gingival displacement procedure can lead to clinically improved fixed restorations, less patient chair time, and less patient discomfort.

Materials and Methods: One hundred (100) patients will be recruited from the University of North Carolina (UNC) School of Dentistry (SOD). A stratified block randomization will be used to randomize patient to impression technique: Aquasil Ultra Cordless, Dentsply International using Aquasil Ultra Polyvinyl siloxane (PVS) impression material versus Dentsply International, gingival displacement cord (Ultrapak, Ultradent Products International) hydrated with aluminum chloride hexahydrate (Hemodent, Premier Dental Products Company). Stratification will be based on the clinic where treatment is provided (Dental Faculty Practice, Graduate Operative Dentistry, Graduate Prosthodontic Clinic), A block size of 4 within each stratum will be used to maintain a balanced allocation to impression group. Patient inclusion criteria include: 1) requires indirect restoration 2) probing depths 4mm or less. 3) No bleeding on probing. 4) finish line 0-1mm sub-gingival.

Specific Aims

The intent of this exploratory study is to compare two methods (cordless vs corded gingival displacement) currently used in clinical practice to displace sulcular tissues to facilitate an acceptable dental impression that accurately captures the prepared cervical finish line for the fabrication of indirect fixed prosthodontic restorations. The primary aims are to compare the two methods with respect to 1) the accuracy of the impression with respect to capturing the prepared cervical finish line for the fabrication of the indirect fixed prosthodontic restoration as assessed by two expert clinicians 2) the time required to prepare the impression and 3) the discomfort of the procedure as reported by the patient. Secondary aims are to estimate the effect of clinician experience (resident level vs faculty) and jaw of restoration placement (maxillary vs mandibular) on the outcomes of accuracy, time, and discomfort.

Significance

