Indirect fixed prosthodontic restorations are widely used for the restoration of teeth. The fabrication of a well-fitting indirect restoration requires an accurate impression which captures the cervical finish line. Dentists have a hard time making proper impressions, with a reported 56% of impressions sent to labs being inadequate. The most common deficiency is inadequate recording of the cervical finish line. The primary reason for this inadequacy is deficient gingival displacement technique.

The traditional procedure used to displace gingival tissue prior to making impressions is gingival retraction cord, with a reported 92% of dentists surveyed employing this procedure. (Ahmed 2014) For this procedure to work properly, it is time consuming (requires 7-10 minutes in the sulcus), technique sensitive, requires anesthetizing the patient, and causes patient discomfort both during and post operatively.

More effective and efficient gingival displacement procedure can lead to clinically improved fixed restorations, less patient chair time, and less patient discomfort.

The specific aims in this proposal explore whether a cordless gingival displacement procedure can properly displace sulcular tissues to facilitate an acceptable impression that accurately captures the prepared cervical finish line for the fabrication of indirect fixed prosthodontic restorations and thereby improve the efficiency of a traditionally technique sensitive procedure in dentistry.

Methods

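### The discomfort ratings ask only about the present moment and none is clearly scheduled during displacement, so primary aim 3 is measured incompletely

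*Combined protocol and SAP*

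**What the plan says.** Specific Aims gives the third primary aim as a comparison on "the discomfort of the procedure as reported by the patient". Significance motivates it by saying that retraction cord "causes patient discomfort both during and post operatively".

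Methods specifies one item, "How much discomfort are you experiencing at this point in treatment", answered on a FACES scale from 1 to 10. The first two ratings are taken "at the beginning of the treatment appointment, immediately before the impression procedure is initiated". The other two are taken "immediately after the impression procedure is completed, and again at the completion of the treatment appointment". On the endpoint, Methods states: "The total score indicated by the sum of the 4 questions will be analyzed". Statistical Analysis lists patient discomfort as a primary outcome, tested by the Wilcoxon rank-sum test.

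In the corded arm, step 2 packs two cords and says "These cords will be left in place for a minimum of 8 minutes". Step 3 then removes the larger cord before the impression. In the cordless arm, step 3b places a tip in the sulcus and floods it with impression material.

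**The concern.** The arms differ in how the gingiva is displaced: two packed cords and a wait of at least 8 minutes, against a tip and material delivered into the sulcus. The item does not ask about that interval. It asks how the patient feels at the moment of asking, and the moments chosen are not clearly inside the interval. A patient who found cord packing very unpleasant, but feels comfortable once the tray is out, can truthfully report no discomfort at the third and fourth ratings.

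What is at stake is the interpretation of a primary outcome. A result of no difference could mean that the techniques cause similar discomfort, or only that any difference had passed by the time the question was put. The data as planned could not separate the two. This is distinct from the question of which ratings to sum: the third rating alone, even adjusted for the second, would still ask only about the present.

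**Working it through.** **Plan's own figure.** There is none for discomfort. The only sample size calculation concerns total errors. It reproduces with Noether's formula: n per arm = (1.960 + 0.842)² / (6 × (0.709 − 0.5)²) = 7.849 / 0.2621 = 29.95, rounded up to 30. It has no bearing on this point, so the check is a comparison of the rating times with the procedure steps.

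**Step 1: wording.** The item is in the present tense and tied to the moment of asking. It does not refer back to anything just completed. Each rating therefore covers only its own instant.

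**Step 2: where the ratings fall.** This depends on when the impression procedure starts, and Methods supports two readings.

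- *Reading A: it includes displacement.* The numbered lists are headed as the corded and the cordless impression procedure, and each list contains the displacement steps. Methods also says, for the time outcome, that start and end are defined in those lists.
- *Reading B: it means impression taking only.* The sentence introducing the lists names displacement procedures and impression procedures as two things. Later paragraphs on clinician training and on treatment also name them separately.

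| Rating | Reading A, both arms | Reading B, corded | Reading B, cordless |
|---|---|---|---|
| 1, start of appointment | before technique | before technique | before technique |
| 2, before impression procedure | before technique | cord in the sulcus | before technique |
| 3, after impression procedure | after technique | after technique | after technique |
| 4, end of appointment | after technique | after technique | after technique |
| Ratings within displacement | 0 of 4 | 1 of 4 | 0 of 4 |

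The cordless column is the same under both readings because step 3b displaces the tissue and delivers the impression material in one act; no rating can fall between the two.

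**Step 3: what each reading implies.** Under A, packing and dwell, or the tip, lie between ratings 2 and 3 and are not rated. Under B, rating 2 catches one instant with cord in place in one arm, while in the other arm the same question is a pre-technique baseline. Rating 2 then measures different things by arm, and packing itself is still not rated.

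**Step 4: what is captured.** Ratings 3 and 4 record discomfort that persists after the technique. Set against the rationale, the after part is covered and the during part is not reliably covered.

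**Step 5: size.** A figure would need the between-arm difference during displacement, the part of it still present at rating 3, and the SD of the summed score. The documents give none of these.

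**The case against.** Four objections have weight.

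1. *The aim does not say during displacement.* It speaks of the discomfort of the procedure, and the rationale names discomfort afterwards as well. A reader might infer that the endpoint does not answer aim 3 at all. The documents do not support that, because ratings 3 and 4 address the persisting part. This stands and limits the point to incomplete coverage.

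2. *The count of 0 of 4 is one reading.* It follows from the headings, but the text elsewhere separates displacement from impression. This stands. Reading B is no defence of the schedule, however, since it makes rating 2 asymmetric between arms.

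3. *The direction of any bias is not known.* A reader might infer that the comparison is diluted toward no difference. That assumes the arms differ less after the procedure than during it. No listed step removes the first, smaller cord, so it may still be in the sulcus at rating 3. Customary anesthesia, given as necessary before preparation, may also shrink the difference during displacement. This stands.

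4. *Power figures would not be evidence.* Suppose a 2-point difference during the procedure, SD 2, 50 per arm (100 split equally) and a normal test on one rating. If all, half or a quarter of the difference is still felt at rating 3, the noncentrality, standardised difference × √(50/2), is 5.0, 2.5 or 1.25, and power is about 99.9%, 70% or 24%. Every input except the group size is assumed, and the plan tests the sum of four ratings by Wilcoxon. These figures cannot be read as the loss in this trial.

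It can also be said that momentary ratings avoid recall and keep the wording identical across times. That is true, and it is the main cost of the remedy.

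**Conclusion.** The point holds in a limited form. The item is momentary, no rating is clearly scheduled during displacement, and no item asks about the procedure just completed. Displacement is covered by 0 of 4 ratings if the impression procedure includes it. If not, it is covered by 1 of 4 in the corded arm and none in the cordless arm. The endpoint therefore measures aim 3 incompletely: persisting discomfort is captured, and transient discomfort during displacement, which the protocol's own rationale names, can be missed.

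The conclusion rests on the wording and schedule alone. It does not extend to saying that aim 3 goes unanswered or that the result is biased toward no difference. How much the comparison is affected, and in which direction, cannot be computed from the documents. Because discomfort is a primary outcome and the remedy is cheap, the change should be made even though the study describes itself as exploratory.

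**What to change.** 1. Reword the third rating, or add one item at that time, to ask in the same words in both arms: *How much discomfort did you feel during the gum displacement and impression that were just completed?* Use the same FACES scale. Put it right after the first impression is removed. Methods allows further impressions but evaluates only the first, so this timing keeps the rating tied to the impression that is assessed.
2. Name that rating as the measure for aim 3. The planned Wilcoxon test can be applied to it unchanged. The other momentary ratings can be kept and reported as secondary.
3. State that, for the ratings, the impression procedure starts before displacement in both arms, so that rating 2 is a pre-technique baseline in each.

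**Cost.** One reworded or added question and a short change to the outcome definition, with no extra visit, staff or procedure. The change does replace the four-rating sum as the primary discomfort measure, and this should be stated openly. The new rating relies on recall over a short period. Its wording differs from the momentary ratings, so change from rating 2 is not like-for-like, though rating 2 can still serve as a covariate in the adjusted analysis. Adding an item instead of rewording keeps the four momentary ratings intact, at the price of one more question.
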